## **Design and methods**

### **- Study Design**

This study is a single-blind randomized clinical trial it will perform at the University of Veracruz, Veracruz, Mexico, between February 2017 to October 2018. Young adults students of the University of Veracruz will randomly allocate to a 12-week no consumption of ASBs intervention or control group.

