### **- Randomization and intervention procedure**

All the volunteers that will meet the inclusion criteria will sign the informed consent before the study started. The volunteers will randomly allocate in control or intervention group (1:1 allocation ratio to each group) in blocks of 2 by using Microsoft Office Excell. Nobody involved with data acquisition will have access to de assignment of the subjects. Once randomly assigned, a blood sample and anthropometric variables will take to establish basal data. Participants will interview to know, caloric intake (24-h food recall), consumed portions and beverage consumption (Food frequency questionnaire). The intervention group is not allowed to consume ASBs, however they are allow consuming products that did not contain ASs in their formulae. For the control group ASBs consumption are not modified. Both groups continue the normal food habits.

Anthropometric measures, 24-h food recall and food frequency questionnaire data will collect at week 6 and 12. Blood sample will take once more at study week 12. In order to categorize the physical activity a previously validated questionnaire will apply, the physical level are divide in low, moderate and high.

- **Study population**

Young overweight or obese students between 19 and 27 years old with normally consumption of ASBs

- **Sample**

It is a probabilistic, stratified sampling that is made from the overweight and obese population who consume ASBs.

The data for obtaining the sample will be collected from the questionnaires that will be applied to the students in which we will know who consume ASBs.

- **Statistic**

They will be analyzed with the statistical program SPSS 21. With a two-way analysis of variance ANOVA or T-student test with repeated measures. And the variables will be correlated.

- **Ethical and biosecurity considerations**

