According to the Regulation of the General Health Law on Health Research, which was enacted in 1984 by Miguel de la Madrid in his third article, research for health includes the development of actions that contribute; to the knowledge of the biological and psychological processes of humans, to the knowledge of the links to the causes of illness, the medical practice and the social structure, to the prevention and control of health problems, to the knowledge and evaluation of the harmful effects of health environment, to the study of the techniques and methods that are recommended or used for the provision of health services, and to the production of supplies for health.

According to article 13 of this law, in any investigation in which the human being is subject to the study, the criterion of respect for their dignity and the protection of their rights and welfare must prevail.

According to article 16 in the investigations of human beings the privacy of the individual subject to the investigation will be protected, identifying it only when the result requires it and this authorizes.

According to article 17 in its second section, this research is considered as minimal risk since the risk of data is used through common procedures, physical or psychological diagnostic tests or routine treatments.

For what subject to the law, the informed consent letter will be provided to the research prospectus, which will be delivered prior to the application of the questionnaire. For the application of the questionnaire will pass through each classroom of the Faculty of Nutrition and Biochemistry of the Veracruz University Veracruz campus, which will be carried out after authorization by the authorities of each faculty. Likewise, the subject will be given a clear and concise explanation of the objectives of the research, the benefits, the inconveniences or risks expected the procedures that will be used, its purpose and the previous investigations that have been carried out on the subject, as well as those that arise during the time of the study. This process will be in charge of the main researcher of the project.

The prospect should be aware that he is at liberty to withdraw his consent at any time, and that the information collected during the investigation will be used only by the research group who will replace his name with a code to guarantee the confidentiality of the data.

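### For outcomes measured at three visits, the repeated-measures ANOVA as SPSS normally runs it discards participants who miss week 6 or week 12; a mixed model would keep their data

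*Protocol*

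**What the plan says.** The Statistic paragraph of the protocol fixes the software, "They will be analyzed with the statistical program SPSS 21", and the methods, "With a two-way analysis of variance ANOVA or T-student test with repeated measures". It does not say which test goes with which outcome.

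The Randomization and intervention procedure section sets the visits. Baseline comes after allocation: "Once randomly assigned, a blood sample and anthropometric variables will take to establish basal data". Then "Anthropometric measures, 24-h food recall and food frequency questionnaire data will collect at week 6 and 12", whereas for blood "Blood sample will take once more at study week 12". Anthropometry therefore has three time points and blood markers have two. Diet is also asked about at entry, so it has three as well.

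The Study Design section describes participants as "randomly allocate to a 12-week no consumption of ASBs intervention or control group". The control arm's ASB consumption is left unchanged. Under Ethical and biosecurity considerations, "The prospect should be aware that he is at liberty to withdraw his consent at any time".

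The protocol gives no dropout rate, analysis population or rule for missing data. It does not use the term complete case.

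**The concern.** For two arms and three visits, the natural reading of the named method is a group-by-time repeated-measures ANOVA. In SPSS this is normally run with one row per participant, and a row with any visit missing is deleted. This is general knowledge of the software, not something the protocol states. Someone who leaves after week 6 then loses their baseline and week-6 values from the analysis. Someone who misses only week 6 loses their week-12 value.

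The arms also ask different things of participants: one carries a 12-week prohibition and the other changes nothing. Leaving could therefore be related to early progress in one arm and not in the other. If intervention participants with little change by week 6 leave more often, those who remain look better than the arm as randomised. That error runs in the direction of the protocol's hypothesis, that restriction lowers anthropometric values. The week-6 measurement that could correct for this is collected and then not used for the people concerned.

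**Working it through.** The protocol states no sample size, SD, effect size or dropout rate, so there is no figure of its own to reproduce. Everything numerical below is an assumption chosen to show a range.

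**Step 1. Which analyses lose data already collected?**

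| Analysis | Participant who leaves after week 6 |
|---|---|
| Repeated-measures ANOVA, three visits, one row per person | Deleted, with baseline and week-6 data |
| Paired t-test, baseline to week 6 | Kept, but this is not the week-12 arm comparison |
| Paired t-test, baseline to week 12 | Excluded; one who missed only week 6 is kept |
| Two-way ANOVA on one row per visit | Week-6 row kept, but within-person correlation ignored |
| Any analysis of blood markers | Excluded from the change; no week-6 sample exists to lose |

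**Step 2. Size of the completer bias when leaving depends on the week-6 change.** Assume no true effect and random loss in the control arm. Let z be the standardised week-6 change, with positive values meaning poorer response, and let r be its correlation with the week-12 change. Intervention-arm leaving follows a logistic model in z, calibrated to total loss d. Then

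bias (in SD of week-12 change) = r × E[z | stays].

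E[z | stays], by numerical integration, at d = 10%, 20%, 30%:
- slope 1.0 (odds of leaving about 2.7 times higher per SD): −0.091, −0.173, −0.253
- slope 1.5: −0.122, −0.227, −0.327

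| Slope | r | 10% | 20% | 30% |
|---|---|---|---|---|
| 1.0 | 0.70 | −0.06 | −0.12 | −0.18 |
| 1.0 | 0.75 | −0.07 | −0.13 | −0.19 |
| 1.5 | 0.70 | −0.09 | −0.16 | −0.23 |
| 1.5 | 0.75 | −0.09 | −0.17 | −0.25 |

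With an assumed SD of week-12 weight change of 2.5 kg, slope 1.0 and r = 0.75 give an apparent benefit of about 0.17, 0.32 and 0.47 kg. Halving the slope to 0.5 gives about 0.09, 0.18 and 0.27 kg.

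**Step 3. Effect on the test.** Simulation with 3,000 replicates, slope 1.5, r = 0.7, an assumed 50 per arm and equal loss rates in the two arms (random in control). A two-sided 5% comparison of week-12 change in completers rejects a true null in about 7%, 10% and 16% of trials. Equal dropout rates therefore do not protect if the reasons for leaving differ.

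**Step 4. When the bias vanishes.** At 20% loss and 50 per arm, random leaving gives a bias of 0.003 SD and type I error of 0.046. The same selective mechanism in both arms with no true effect gives 0.003 SD and 0.05.

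**Step 5. What keeping the week-6 data achieves.** A likelihood-based estimate that uses leavers' week-6 values has bias of about 0 in the Step 3 setting. This follows by construction, because leaving there depends only on an observed value. If leaving depends instead on the unseen week-12 value, the results at 10%, 20% and 30% loss are:
- completers: about −0.13, −0.23, −0.32 SD
- keeping week-6 data: about −0.07, −0.13, −0.19 SD

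At 20%, roughly 0.10 of 0.23 SD is removed (0.23 − 0.13).

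**The case against.** The strongest reply is that the protocol nowhere commits to a completer analysis. It names test families and a package, and imputation before the ANOVA would be compatible with that. Missing-data handling is commonly left to a statistical analysis plan, which may exist and is not shown. That stands: the absence of a missing-data rule is not the complaint. The complaint is that the method the protocol does name excludes partial follow-up by default, when a better one is available in the same software.

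A reader might infer more than the documents support:

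- *Every named analysis is complete-case.* It is not. A t-test between two visits does not need the third, and the protocol's wording leaves the choice of test open.
- *Week-6 blood data are lost too.* No week-6 sample is taken.
- *The trial will be biased.* The freedom to withdraw is ordinary consent wording and not evidence of attrition. Nothing in the protocol links leaving to poor early response, and the promised nutritional follow-up and return of results could encourage completion.
- *A mixed model removes the bias.* It does so only when leaving is explained by observed data.

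**Conclusion.** The point holds as a conditional improvement for anthropometric and dietary outcomes. If their analysis is the standard SPSS repeated-measures ANOVA without imputation, participants with an incomplete set of visits are removed with the data they gave. Loss of precision follows whenever anyone misses a visit.

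Bias requires more: leaving must be related to early response, and differently in the two arms. Under assumed intervention-arm loss of 10–30% tied to the week-6 change, with a correlation of 0.7–0.75 and logistic slopes of 1.0–1.5, the bias is about 0.06–0.25 SD of change in favour of restriction. None of these inputs comes from the documents. The bias is about zero with random loss, or with the same mechanism in both arms and no true effect. The change is worth making because it is cheap, not because bias has been shown.

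**What to change.** In the Statistic paragraph, for outcomes measured at baseline, week 6 and week 12:

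1. Replace the repeated-measures ANOVA or t-test with a linear mixed model (SPSS MIXED) with arm, visit, arm-by-visit interaction and the baseline value, and an unstructured covariance across visits.
2. Include all randomised participants with any post-baseline visit, each in the assigned arm.
3. Name the week-12 arm difference as the result.
4. Add a sensitivity analysis for dropout that depends on unseen values, since the mixed model removes only part of that bias.
5. Report by arm the number leaving before week 6. They have no post-baseline data and the model cannot recover them.

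Blood markers need no change on this account.

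The cost is a rewritten statistics sentence and slightly more analysis work in the same software, with no new visits, procedures or participants. The downside is reliance on a missing-at-random assumption, which is nevertheless weaker than the one the completer analysis needs.

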## **Hypothesis**

The restriction of ASBs in young people who consume them and who present overweight and obesity, decrease an anthropometric data, and biochemical markers.

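### The named analyses leave the basal value out as a covariate; adjusting for it would gain precision from data already collected, materially for outcomes with moderate correlation over time and little for very stable ones

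*Protocol*

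**What the plan says.** The Statistic section of the protocol (under Design and methods) names SPSS 21 and then the inferential method: "With a two-way analysis of variance ANOVA or T-student test with repeated measures". The only other analysis is "And the variables will be correlated", which is not an adjusted comparison of arms. No covariate, ANCOVA or other baseline-adjusted model appears.

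The section on randomization and intervention procedure sets the measurement schedule:

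- Basal: "Once randomly assigned, a blood sample and anthropometric variables will take to establish basal data".
- Follow-up of anthropometry and diet: "Anthropometric measures, 24-h food recall and food frequency questionnaire data will collect at week 6 and 12", so three time points with basal.
- Follow-up of blood: "Blood sample will take once more at study week 12", so two time points with basal.

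Allocation is "1:1 allocation ratio to each group) in blocks of 2". Such blocks balance the numbers per arm, not the basal values. The Hypothesis section expects the restriction to "decrease an anthropometric data, and biochemical markers", so both groups of outcomes matter. The protocol gives no sample size, SD, correlation or target effect.

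**The concern.** In a repeated-measures ANOVA or a test on change, the basal value enters as one more outcome reading. With two time points this fixes its weight at exactly 1: each participant's basal value is subtracted in full, however well or badly it predicts the week-12 value. ANCOVA estimates that weight from the data.

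Two things are at stake. The first is precision: the confidence interval for the arm difference is wider than the collected data require. The second is accuracy given the arms actually obtained: if they happen to differ at basal, full subtraction over-corrects whenever the true weight is below 1. A participant with a high basal reading tends to fall back somewhat without any intervention, and the change score counts that fall as change.

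**Working it through.** The protocol states no figure on this point, so there is nothing to reproduce first. The number of time points comes from the protocol. The correlation rho, equal SDs (sigma) at both times, and the sample sizes and effects used as illustrations are assumptions.

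**1. Equivalence for blood markers.** With two arms and two time points, the arm-by-time F of a repeated-measures ANOVA equals the squared two-sample t on change. On one simulated data set, both came to 0.1461.

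**2. Variance.** In units of sigma²(2/n), with n per arm, the variance of the arm difference is:

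- change score: 2(1-rho)
- ANCOVA: 1-rho² = (1-rho)(1+rho)
- ratio ANCOVA/change: (1+rho)/2

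**3. Shift given a basal difference D.** For a true effect theta, the expected week-12 difference given D is theta + rho·D. The change score subtracts D and leaves theta - (1-rho)D. ANCOVA subtracts rho·D and leaves theta.

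**4. Numbers.** The n per arm assumes a 0.5 SD difference, two-sided alpha 0.05 and 80% power.

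| rho | Var. change | Var. ANCOVA | Ratio | Extra variance of change | n per arm, change / ANCOVA | Shift of change estimate if D = 0.3 SD |
|---|---|---|---|---|---|---|
| 0.5 | 1.0 | 0.75 | 0.75 | 33% | 63 / 48 | -0.15 SD |
| 0.7 | 0.6 | 0.51 | 0.85 | 18% | 38 / 33 | -0.09 SD |
| 0.9 | 0.2 | 0.19 | 0.95 | 5% | 13 / 12 | -0.03 SD |
| 0.95 | 0.1 | 0.0975 | 0.975 | 2.6% | 7 / 7 | -0.015 SD |

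**5. Simulation check** (20,000 trials, 30 per arm, rho 0.6, no effect). Both estimators averaged about 0. The slope of the estimate on the basal difference was -0.39 for the change score (theory -0.40) and 0.01 for ANCOVA (theory 0). The variance ratio was 0.83 against a theoretical 0.80; the gap reflects the small-sample cost of estimating the slope, plus simulation error.

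**6. Three-visit outcomes.** If the arm-by-time interaction over basal, week 6 and week 12 were the test, it would be a joint test on 2 df. Power was simulated with 30 per arm, equal correlations between visits and half the week-12 effect present at week 6:

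| rho | Week-12 effect | 2-df interaction | Week-12 change | Week-12 ANCOVA |
|---|---|---|---|---|
| 0.5 | 0.5 SD | 37% | 48% | 58% |
| 0.7 | 0.5 SD | 58% | 68% | 74% |
| 0.9 | 0.25 SD | 46% | 57% | 58% |

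The step from the first power column to the second is the price of the omnibus test. Only the step from the second to the third is due to the missing covariate, and it almost vanishes at rho 0.9.

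**The case against.** *The protocol leaves this open.* It names neither the factors nor the contrast, the primary outcome or the time point, and a statistical analysis plan that is not shown could add covariates. This stands in part. The protocol does name its inferential methods, though, and they are unadjusted, so the point concerns a stated choice and not a gap.

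*A change-score comparison is valid.* This stands. A reader might infer that the planned analysis is biased or invalid. It is not: over repeated randomisation the estimate is unbiased, and the shift of -(1-rho)D is conditional on the basal difference that happens to occur.

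*The gain may be negligible for weight and waist.* This stands if their rho over 12 weeks is 0.9 or more, where the variance falls by 5% or less. It does not dispose of the blood markers or other outcomes, whose rho may be lower.

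*The arm main effect would have very low power.* A reader might infer that the plan rests on that effect, which averages in the basal visit. Nothing in the protocol says that it will be interpreted, so its power is no measure of this plan. Nor can the trial be called small, with chance imbalances therefore common, since no sample size is given.

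*The basal value might itself be affected by the intervention.* This stands as a precondition. Basal data are taken after assignment, and the protocol does not say that they precede the restriction. It does not favour the change score, however. If the restriction had already moved the basal value by delta, then with equal SDs the change score would lose all of delta and ANCOVA rho·delta.

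**Conclusion.** The point holds as an improvement in efficiency and in conditional accuracy, not as an error that invalidates the analysis. For two-time-point blood markers, the between-arm test available under the named methods is a change-score comparison. Under equal SDs its variance exceeds that of ANCOVA by 33% at rho 0.5, 18% at 0.7, 5% at 0.9 and 2.6% at 0.95. The benefit is therefore material for outcomes with moderate rho and small for very stable ones. Which outcomes fall where cannot be settled from the protocol.

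The direction does not depend on equal SDs. With SDs s0 (basal) and s1 (week 12), the change-score variance is s1²(1-rho²) + (s0 - rho·s1)², which is never below the ANCOVA term s1²(1-rho²). The only offset is the small cost of estimating the slope.

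The further loss of power from a 2-df interaction in three-visit outcomes is a separate matter and arises only if that test is used.

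**What to change.** Replace the method sentence in the Statistic section along these lines:

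- Each outcome at week 12 is compared between arms in a linear model with arm and the basal value of that outcome, and reported as an adjusted mean difference with 95% CI.
- For outcomes also measured at week 6, weeks 6 and 12 are modelled together as outcomes, with the basal value as covariate and arm-by-visit terms, and the week-12 contrast is reported.

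In the section on randomization and intervention procedure, state that basal measurements, although taken after assignment, are completed before the restriction begins; the adjustment relies on this. Naming week 12 as the target is itself a choice that the protocol has not made, and the sponsor should confirm it. Record the change before outcomes are compared by arm.

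The cost is a few sentences and one degree of freedom per basal covariate. The models run in SPSS 21, and no new measurements or participants are needed. Confirming when basal data were taken relative to the start of the restriction is the one extra task.
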